
Event	Management
Immune-related neuropathy, Grade 1	
 • Continue atezolizumab. • Investigate etiology.
Immune-related neuropathy, Grade 2	
 • Withhold atezolizumab for up to 12 weeks after event onset.^a • Investigate etiology. • Initiate treatment as per institutional guidelines. • If event resolves to Grade 1 or better, resume atezolizumab.^b • If event does not resolve to Grade 1 or better while withholding atezolizumab, permanently discontinue atezolizumab and contact
Immune-related neuropathy, Grade 3 or 4	
 • Permanently discontinue atezolizumab and contact the Sponsor.^c • Initiate treatment as per institutional guidelines.
Myasthenia gravis and Guillain-Barré syndrome (any grade)	
 • Permanently discontinue atezolizumab and contact the Sponsor.^c • Refer subject to neurologist. • Initiate treatment as per institutional guidelines. • Consider initiation of 1–2 mg/kg/day oral or IV prednisone or equivalent.
Immune-related meningoencephalitis, all grades	
 • Permanently discontinue atezolizumab and contact the Sponsor.^c • Refer subject to neurologist. • Initiate treatment with 1–2 mg/kg/day IV methylprednisolone or equivalent and convert to 1–2 mg/kg/day oral prednisone or equivalent upon improvement. • If event does not improve within 48 hours after initiating corticosteroids, consider adding an immunosuppressive agent. • If event resolves to Grade 1 or better, taper corticosteroids over ≥ 1 month.

IV=intravenous

- Atezolizumab may be withheld for a longer period of time (ie, >12 weeks after event onset) to allow for corticosteroids (if initiated) to be reduced to ≤ 10 mg/day oral prednisone or equivalent. The acceptable length of the extended period of time must be agreed upon by the investigator and the Sponsor.
- If corticosteroids have been initiated, they must be tapered over ≥ 1 month to ≤ 10 mg/day oral prednisone or equivalent before atezolizumab can be resumed.
- Resumption of atezolizumab may be considered in subjects who are deriving benefit and have fully recovered from the immune-related event. Subjects can be rechallenged with atezolizumab only after approval has been documented by both the investigator (or an appropriate delegate) and the Sponsor.

Table 22: Diagnostic Criteria and Management for Systemic Immune Activation

Systemic Immune Activation		
Systemic immune activation criteria apply only when alternate etiologies have been excluded		
Major Criteria	Minor Criteria	

 • Fever $\geq 38.5^{\circ}\text{C}$ (on more than one occasion) • Ferritin > 3000 ng/mL • Cytopenias: \geq Grade 2 in two or more lineages • ≥ 2 age-adjusted SD elevation soluble IL-2 receptor • Severe multi-organ dysfunction • Decreased fibrinogen 	
 • Splenomegaly • Hemophagocytosis BM, spleen or LN • Elevated GGT or LFTs (AST/ALT/tBili) • Elevated triglycerides • Elevated LDH • Decreased natural killer-cell activity 	
Number of Criteria	Management	
Consistent with systemic immune activation	4 major criteria	Consider tocilizumab (4 mg/kg IV) and Solumedrol [®] (methylprednisolone) (1g IV QD). Contact the Sponsor for additional recommendations. Consider HLH-94 protocol if no clinical improvement.
Probable systemic immune activation	3 major criteria OR 2 major criteria AND 3 minor criteria	Depending on clinical severity, subject can be treated as per “Consistent with systemic immune activation” or “Possible systemic immune activation” case definition. Contact the Sponsor for additional recommendations
Possible systemic immune activation	1 major criteria AND 4 minor criteria	Consider Solumedrol [®] (1g IV QD) Contact the Sponsor for additional recommendations. As per “Consistent with systemic immune activation” recommendations if no improvement or clinically worsening

BM = bone marrow; GGT = gamma-glutamyl transpeptidase; IL-2 = interleukin-2; IV = intravenous; LFT = liver function test; LN= lymph node; QD = once daily; tBili = total bilirubin.

Notes: Criteria adapted from a Delphi Survey of 26 experts regarding helpful criteria in the positive diagnosis of Hemophagocytic Syndrome in adult subjects (Hejblum G. et al PLoS One [Public Library of Science] April 2014; Volume 9, Issue 4). Standard-of-care for systemic immune activation has not been established. Case reports and recommendations have been published for cytokine release syndrome (Lee 2014, Maude 2014, Teachey 2013),^{28, 29, 49} and based on etiologic similarities, these practices have been incorporated into the above treatment recommendations.

These recommendations do not replace clinical judgment and are intended as suggested guidance.

Table 23: Management Guidelines for Immune-Related Nephritis

Event	Management

NSCLC	non-small cell lung cancer
ORR	overall response rate
OS	overall survival
PD	progressive disease
PD-1	programmed death-1
PD-L1	programmed death-ligand 1
PFS	progression-free survival
PI	proteasome inhibitor
PK	pharmacokinetic(s)
PR	partial response
PT	preferred term
PrT	prothrombin time

PTT	partial thromboplastin time
RECIST	response evaluation criteria in solid tumors
SAD	short axis diameter
SAE	serious adverse event
SD	stable disease
SET	study evaluation team
SIPPM	site investigational product procedures manual
SOC	system organ class
SPD	sum of the products of the two largest perpendicular diameters
STD	Standard deviation
SUSAR	suspected unexpected serious adverse reaction
TEAE	treatment-emergent adverse event
ULN	upper limit of normal
VGPR	very good partial response

1. INTRODUCTION

This statistical analysis plan (SAP) contains definitions of the analysis population(s), derived variables and statistical methods for Study 54767414 LUC2001.

1.1. Trial Objectives

Primary Objective

The primary objective of this study is to compare the overall response rate (ORR) in subjects treated with daratumumab in combination with atezolizumab versus atezolizumab alone.

Secondary Objectives

- To assess the safety of the combination of daratumumab and atezolizumab
- To compare the duration of response (DoR) in subjects treated with daratumumab in combination with atezolizumab versus atezolizumab alone
- To compare the clinical benefit rate (CBR) in subjects treated with daratumumab in combination with atezolizumab versus atezolizumab alone
- To compare progression-free survival (PFS) in subjects treated with daratumumab in combination with atezolizumab versus atezolizumab alone
- To compare overall survival (OS) in subjects treated with daratumumab in combination with atezolizumab versus atezolizumab alone
- To evaluate the pharmacokinetic and immunogenicity profile of daratumumab when given in combination with atezolizumab
- To evaluate the pharmacokinetic and immunogenicity profile of atezolizumab when given in combination with daratumumab

Exploratory Objectives

- To compare ORR evaluated by the Immune-Related Response Evaluation Criteria in Solid Tumors (irRECIST)
- To explore biomarkers predictive of response to therapy
- To evaluate potential pharmacodynamic biomarkers in response to therapy
- To explore the relationships between pharmacokinetics, pharmacodynamics, adverse event profiles, and clinical activity of daratumumab given in combination with atezolizumab in subjects with previously treated advanced or metastatic NSCLC
- To explore the benefit of daratumumab and atezolizumab treatment in subjects who had confirmed disease progression on atezolizumab monotherapy

1.2. Trial Design

The study begins with a 6-subject safety run-in cohort to be evaluated by the Study Evaluation Team (SET). After evaluation, if SET has determined that the combination therapy of daratumumab and atezolizumab are safe and tolerable, the study will proceed to the randomization phase in which 90 subjects are randomized into the two treatment arms

stratified by PD-L1 expression status (IC0 and TC0 vs. others), histology (squamous vs. non-squamous), and number of previous lines of therapy received (1 or >1):

Arm A: atezolizumab; Arm B: atezolizumab + daratumumab.

[figure not shown]
Subjects in Arm A (treated with atezolizumab monotherapy) who have confirmed disease progression based on RECIST 1.1 may cross over to Arm B and receive daratumumab and atezolizumab after crossover eligibility criteria are met.

An internal Janssen Data Monitoring Committee (DMC), independent of the study team, will be established to review the efficacy and safety data in the randomization phase. The DMC will review the totality of data after approximately 40, 60, and 90 subjects have been enrolled, including activity within distinct PD-L1 expression subgroups. Based on these findings, the DMC may formulate recommendations on study conduct, including the expansion of enrollment of some PD-L1 subgroups, resulting in greater than 96 subjects. The DMC may request additional ad-hoc reviews as data accumulate.

For subjects in Arm A, Atezolizumab will be administered at 1200 mg IV on Day 1 of every 21-day cycle. For subjects in the safety run-in cohort and in Arm B, Daratumumab will be administered intravenously (IV) at 16 mg/kg weekly on Days 1, 8, and 15, for the first 3 cycles, then on Day 1 of each 21-day cycle thereafter. Atezolizumab for these subjects will be administered at 1200 mg IV on Day 2 of Cycle 1 and on Day 1 of every 21-day cycle thereafter. Pre-infusion medication is administered before first infusion of study medication to prevent infusion-related reactions. Post-infusion medication is administered to reduce the risk of delayed infusion reactions in all subjects.

The combination therapy and the monotherapy will continue until treatment discontinuation due to disease progression, unacceptable toxicity, or other protocol-defined treatment discontinuation criteria. Subjects enter the Follow-up phase after the End-of-Treatment visit, or 30 (+7) days after the discontinuation of the study drugs. Subjects will be followed for survival every 12 weeks after confirmed disease progression or start of new anticancer therapy.

The end of the study is anticipated to be 6 to 12 months after the last subject has been enrolled (last subject in) or when the last subject has the last assessment in this study (eg, last survival follow-up for the last subject), whichever occurs first, and the study may be extended to allow for further treatment and follow-up of subjects.

Figure 1: Schematic Overview of the Study Design

1.3. Statistical Hypothesis for the Primary Objective

The primary hypothesis is that the combination therapy of atezolizumab with daratumumab will significantly improve ORR compared to atezolizumab monotherapy in subjects with NSCLC.

1.4. Sample Size Determination

A 6-subject safety run-in cohort will be evaluated by the Safety Evaluation Team to determine the safety and tolerability of atezolizumab administered in combination with daratumumab before proceeding with the randomized phase of the study.

For the randomization part, assuming that the ORR for atezolizumab monotherapy is approximately 20%, and the addition of daratumumab would improve ORR by 20% to 40%, 90 subjects need to be randomized with a 1:1 ratio in order to achieve 80% power to detect this difference with a one-sided alpha of 0.10. If benefit from the combination is not observed across the overall study population, targeted enrollment of subgroups, based on tumor PD-L1 expression level, may be implemented, based on DMC recommendations. As such, approximately 50 additional subjects in the TC2/TC3 subgroups may be enrolled to preliminarily evaluate the treatment effect. If the ORR is 25% for atezolizumab monotherapy and 50% for the

atezolizumab + daratumumab combination in the TC2/TC3 subgroup, the lower bound of the 90% CI for the difference in ORR would exclude 0 (i.e., a positive signal in favor of the combination).

1.5. Randomization and Blinding

Central randomization will be implemented following the safety run-in evaluation. Subjects will be randomly assigned to 1 of 2 treatment arms based on a computer-generated randomization schedule prepared before the study by or under the supervision of the sponsor. The randomization will be balanced by using randomly permuted blocks and will be stratified by centrally determined PD-L1 expression status (TC0 and IC0 vs. others), histology (squamous vs. non-squamous), and number of prior therapies (1 vs >1).

2. GENERAL ANALYSIS DEFINITIONS

All tabular summaries will be presented by treatment group. Categorical data will be summarized by the number and percentage of subjects falling within each category. Continuous variables will be summarized by descriptive statistics including N, mean, standard deviation, median, minimum, and maximum.

2.1. Baseline, Relative Day

Baseline value is defined as the last non-missing value obtained prior to the first dosing date/time of study medication.

Day 1 is the first dosing date of study medication. Study Day is defined as assessment date – first dose date + 1 for any assessment done on or after first dose date; otherwise, study day is defined as assessment date – first dose date.

Unless specified otherwise, data to be analyzed or presented over time will be presented by visit and time point (as appropriate) that are recorded in the eCRF.

2.2. Pooling Algorithm for Analysis Centers

Data from all study centers will be pooled for analyses.

2.3. Analysis Sets

2.3.1. Intent-To-Treat Analysis Set

Intent-to-Treat (ITT) analysis set includes all subjects who have entered the randomization phase of the study. Subject information, demographics, baseline disease characteristics, and efficacy summaries will be based on this analysis set.

2.3.2. Safety Analysis Set

Safety analysis set includes all subjects who have received at least 1 administration of any study medication. This analysis set will be used for all exposure and safety analyses.

2.3.3. Response-evaluable Analysis Set

Response-evaluable analysis set includes all randomized subjects who have received at least 1 administration of study medication and have at least 1 adequate post baseline disease assessment. Response related endpoints will also be analyzed based on this analysis set as appropriate.

2.3.4. DLT Analysis Set

Dose-limiting Toxicity (DLT) analysis set includes any subject in the safety run-in phase who has a DLT regardless of dose received or who did not have a DLT but received at least 75% of the planned dose during the DLT evaluation period, which is 21 days starting from the day of the first dose of study drug.

Criteria for DLT are listed in Attachment 1. This analysis set will be used to summarize the dose-limiting toxicity.

2.3.5. Safety Run-in Analysis Set

Safety run-in analysis set includes all subjects in the safety run-in phase who have received at least 1 administration of study medication.

2.3.6. Immunogenicity-evaluable Analysis Set

The immunogenicity-evaluable analysis set includes all subjects who receive at least 1 dose of atezolizumab or daratumumab and have appropriate samples for detection of antibodies to atezolizumab or daratumumab. This analysis set will be used for immunogenicity related analyses.

2.3.7. Pharmacokinetics-evaluable Analysis Set

Pharmacokinetics-evaluable analysis set includes all subjects who have received at least 1 dose of daratumumab or atezolizumab and have at least 1 post-infusion sample collected. This analysis set will be used for PK analyses.

2.4. Definition of Subgroups

The following subgroups are to be performed for exploratory efficacy and/or safety analyses. Additional subgroup analyses may be planned if deemed necessary.

Subgroup	Definition	Analysis Type
Sex	Male, Female	Efficacy, Safety
Age	< 65, ≥ 65	Efficacy, Safety
Race	White, Other	Efficacy, Safety
PD-L1 expression status	Negative (IC0 and TC0), High (TC3 and IC any), Low (others), based on SP-142 assay	Efficacy

2.5. Imputation of Missing Data

Data imputation will be limited and detailed rules will be specified in DPS.

2.6. Other General Definitions

2.6.1. Treatment Groups

The treatment groups are atezolizumab (Arm A) and atezolizumab + daratumumab (Arm B).

2.6.2. Month and Year

One year equals to 365.25 days. One month equals to 365.25/12 days.

2.6.3. Years since Initial NSCLC Diagnosis

This is calculated as date of first dose – date of initial NSCLC diagnosis + 1, divided by 365.25.

2.6.4. Total Dose Received

For Daratumumab, total dose (mg/kg) is the sum of the administered doses per kilogram at each visit, which is calculated as the total dose (mg) recorded on the eCRF divided by body weight (kg) at that visit. For Atezolizumab, total dose (mg) is the sum of the administered doses at each visit, which is calculated as the total dose (mg) recorded on the eCRF.

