6.1.2. Daratumumab Treatment Schedule and Administration

Daratumumab will be administered on Days 1, 8, and 15, for the first 3 cycles, then on Day 1 of each 21-day cycle thereafter until one or more treatment discontinuation criteria are met (eg, disease progression or unacceptable toxicity).

Daratumumab will be administered IV at 16 mg/kg. Each subject's dose will be calculated based on the subject's weight at Cycle 1 Day 1 rounded to the nearest kilogram. The dose of daratumumab will remain constant throughout the study, unless the subject's weight changes more than 10% from Cycle 1 Day 1. All infusions will be planned as outpatient visits. Subjects will receive preinfusion medications and postinfusion medications as outlined in Section 6.1.3.

The dilution volumes, initial infusion rates, and increment of infusion rates for the first, second, and subsequent doses in the absence of an infusion-related reaction >Grade 1 are provided in Table 7. The first infusion, with a volume of 1,000 mL, takes approximately 8 hours; the second and subsequent infusions, with volumes of 500 mL, take approximately 4 hours. The maximum infusion rate for all infusions is 200 mL/hour. The Sponsor may modify the infusion rates or the preinfusion medications prospectively based upon the information collected to date from this and other studies.

Table 7: Daratumumab Infusion Rates

	Dilution Volume	Initial Infusion Rate (first hour)	Incremental Increases in Infusion Rate^a	Maximum Infusion Rate
First infusion	1000 mL	50 mL/hour	50 mL/hour every hour	200 mL/hour
Second infusion^b	500 mL	50 mL/hour	50 mL/hour every hour	200 mL/hour
Subsequent infusions^c	500 mL	100 mL/hour	50 mL/hour every hour	200. mL/hour

- Consider titration of the infusion rate only in the absence of infusion reactions.
- Dilution volume of 500 mL should be used only if there were no Grade 1 (mild) or greater infusion reactions during the first 3 hours of the first infusion. Otherwise, continue to use a dilution volume of 1000 mL.
- Use a modified initial rate for subsequent infusions (ie, third infusion onwards) only if there were no Grade 1 (mild) or greater infusion reactions during a final infusion rate of ≥ 100 mL/hr in the first two infusions. Otherwise, continue to use instructions for the second infusion.

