6.1.4. Dose Delay and Modification

Dose modification of daratumumab is not permitted. Dose delay is the primary method for managing daratumumab-related toxicities.

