2.6.7. Relative Dose Intensity

For Daratumumab, the relative dose intensity (%) is the ratio of total dose received (mg/kg) and total planned dose (mg/kg), calculated as the planned dose times the number of administered infusions. For Atezolizumab, the relative dose intensity (%) is the ratio of total dose received (mg) and total planned dose (mg), calculated as the planned dose times the number of administered infusions.

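### Daratumumab relative dose intensity divides mg given by visit weight, although the mg dose is set on Cycle 1 Day 1 weight, so a full per-protocol infusion can score from 90.9% to 111.1%

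*SAP*

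**What the plan says.** **How the dose is set (protocol 6.1.2).** "Daratumumab will be administered IV at 16 mg/kg". The mg amount is calculated from the subject's "weight at Cycle 1 Day 1 rounded to the nearest kilogram". "The dose of daratumumab will remain constant throughout the study", with one exception: it may change if the subject's "weight changes more than 10% from Cycle 1 Day 1". Protocol 6.1.4 adds: "Dose modification of daratumumab is not permitted".

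**How the dose received is derived (SAP 2.6.4).** Total daratumumab dose in mg/kg is a sum over visits. Each term comes from a rule "which is calculated as the total dose (mg) recorded on the eCRF divided by body weight (kg) at that visit".

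**How relative dose intensity is derived (SAP 2.6.7).** For daratumumab, it is "the ratio of total dose received (mg/kg) and total planned dose (mg/kg"). The planned total is the planned dose multiplied by the count of infusions given.

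**Where it is reported.** SAP 4.4 summarises total dose, number of infusions and relative dose intensity for each drug. SAP 4.3 (Treatment Compliance) has no content of its own and points to 4.4.

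**The concern.** The numerator and the plan rest on different weights. The mg amount is tied to one weight at the start of treatment. The SAP re-expresses it per kg of whatever the subject weighs on the day, then divides by a nominal 16 mg/kg. A reader will take relative dose intensity as the share of the prescribed dose that was delivered. As defined, it is that share multiplied by the ratio of starting weight to current weight.

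The other rules leave few reasons for this ratio to depart from 100%. Daratumumab dose modification is not allowed, and the denominator counts only infusions that were given, so a missed dose drops out. Apart from dosing errors and rounding, an incomplete infusion is the main thing the ratio could show. Weight change adds a shift of up to about ten percentage points to that signal, in either direction. The mismatch lies in the numerator and would remain whatever count of infusions was used below the line.

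**Working it through.** The documents state no value for total dose or relative dose intensity, so there is no figure to reproduce. The check is arithmetic on the definitions.

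**Inputs**
- Planned dose per infusion: 16 mg/kg (protocol 6.1.2).
- Dosing weight W0: Cycle 1 Day 1 weight, rounded to the nearest kg (protocol 6.1.2).
- Range with no change in the mg dose: visit weight Wv from 0.90 to 1.10 times W0 (protocol 6.1.2).
- Divisor for dose received: Wv (SAP 2.6.4). Weight is measured on dosing days (protocol Table 1), so the derivation can run as written.
- Planned total: 16 mg/kg × number of infusions given (SAP 2.6.7).

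**Per infusion, full protocol dose, rounding ignored**

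mg given = 16 × W0. Dose received = 16 × W0 / Wv. Relative dose intensity = (16 × W0 / Wv) / 16 = W0 / Wv.

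| Weight change | mg/kg by SAP 2.6.4 | Relative dose intensity |
|---|---|---|
| 10% loss | 16 / 0.90 = 17.78 | 111.1% |
| 5% loss | 16 / 0.95 = 16.84 | 105.3% |
| none | 16.00 | 100.0% |
| 5% gain | 16 / 1.05 = 15.24 | 95.2% |
| 10% gain | 16 / 1.10 = 14.55 | 90.9% |

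**Per subject**

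A subject's value is the mean of W0 / Wv over the infusions given. The first infusion is at W0 and scores 100%, so the subject's value lies inside the limits above. Cycles 1 to 3 contain 3 × 3 = 9 daratumumab infusions.
- Immediate 10% gain, held: (1 + 8/1.10) / 9 = 91.9%.
- Immediate 10% loss, held: (1 + 8/0.90) / 9 = 109.9%.
- Linear drift to a 10% gain or loss by the last infusion, the mean of 1 / (1 ± 0.10 × i/8) for i = 0 to 8: 95.3% and 105.4%.
- For 25 infusions, the immediate-shift values are 91.3% and 110.7%. The linear-drift values are unchanged to one decimal.

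**Rounding to whole kg**

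At 50.5 kg rounded up, 51/50.5 = 101.0%, which extends the upper limit to 101.0/0.90 = 112.2%. At 50.49 kg rounded down, 50/50.49 = 99.0%, which extends the lower limit to 99.0/1.10 = 90.0%. Rounding adds about one point at this weight and less in heavier subjects.

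**Partial infusion with weight loss**

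90% of the prescribed mg given at 10% weight loss: 0.90 / 0.90 = 100%.

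**With the weights matched**

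Dividing by the rounded dosing weight gives 16 × W0 / W0 = 16 mg/kg, so a full infusion scores 100% at any visit weight. The 90% infusion above then scores 90%.

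**The case against.** Much of the case on the other side is sound.

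- **mg per kg of current weight is a real quantity.** A subject who has lost weight did receive more daratumumab per kg of current weight, so SAP 2.6.4 taken alone is a defensible description of exposure. This stands. The fault appears only when SAP 2.6.7 compares that figure with a plan set on another weight.
- **91% and 111% are limits for a single infusion at the edge of the tolerated weight range.** This stands. Subject-level values lie inside them, and gradual drift roughly halves the spread.
- **The ratio is not the only compliance information.** A reader might infer that SAP 4.3 leaves nothing else and that under-delivery is therefore hidden. The documents do not support that. SAP 4.4 also reports treatment duration, cycles, infusion counts and actions taken at infusions with reasons. SAP 6.1.1 tabulates infusions delayed, skipped, interrupted or aborted because of treatment-emergent events, and SAP 4.5 covers major deviations. The offset occurs within one ratio, although those other summaries do not say how much of a dose was lost.
- **No analysis links dose to death.** A reader might infer a false exposure-harm pattern, because protocol 1.4 records more deaths in the combination arm. No planned analysis relates total dose or relative dose intensity to death. The exposure-response modelling in protocol 11.7 is optional and uses serum concentrations. Early death also lowers cumulative total dose by ending treatment. The documents give no weight-change data and do not describe weight loss as a marker of deterioration.

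These points narrow the consequences. None of them reconciles the two weights, and no other section of either document does so.

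**Conclusion.** Wrong as written, with minor severity. As a measure of adherence to the prescribed dose, daratumumab relative dose intensity carries a factor of W0 / Wv that has nothing to do with adherence. For a full per-protocol infusion it ranges from 90.9% to 111.1%, and whole-kg rounding can add about one point. At subject level it is about 95% to 105% with linear drift to 10%, and about 92% to 110% over nine infusions with an immediate, sustained 10% shift.

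These ranges assume that the mg dose is left unchanged for any weight change up to and including 10%, as protocol 6.1.2 states. How far actual values will move depends on weight changes in the trial, which the documents do not give; the drift patterns above are illustrations.

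The effect is confined to the descriptive daratumumab exposure summary for run-in, Arm B and crossover subjects. Atezolizumab is a flat mg dose and is unaffected. No efficacy estimate, error rate or adverse event count depends on this ratio.

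**What to change.** In SAP 2.6.7, and in the SAP 2.6.4 input to it, define daratumumab relative dose intensity as total mg given over total mg prescribed for the infusions counted. Equivalently, divide the mg given by the weight used to calculate that dose: the rounded Cycle 1 Day 1 weight, or the recalculation weight after a change above 10%. If mg/kg at visit weight is of interest, keep it as a separate, labelled exposure line and do not feed it into relative dose intensity.

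The change concerns the analysis definition only and leaves the dosing rule as it is. The weights are already collected, so the cost is a short SAP edit and one reprogrammed derivation.
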